#### 9.5.7.1.1.3 Non-serious Adverse Event Definition

A non-serious AE includes any AE that is not described in the previous SAE category.

#### 9.5.7.1.1.4 Unexpected Adverse Event Definition

An AE or suspected adverse reaction is considered unexpected if it is not listed in the Reference Safety Information section of the Investigator's Brochure or is not listed with the specificity or

TEPEZZA (HZN-001) Protocol: HZNP-TEP-001 Version 5.0, Amendment 4

severity that has been observed. Unexpected, as used in this definition, also refers to AEs or suspected adverse reactions that are mentioned in the Reference Safety Information as occurring with a class of drugs or as anticipated from the pharmacological properties of the drug, but are not specifically mentioned as occurring with the particular drug under investigation.

### 9.5.7.1.1.5 Adverse Events of Special Interest

Based on previous clinical experience with TEPEZZA, the following AESIs are identified for this study (See Section 7.1.3.4.4.4 for further information):

- Hyperglycemia
- Hearing impairment
- Infusion reaction
- New onset or exacerbation of IBD

#### 9.5.7.1.2 Documentation of Adverse Events

Any AEs that occur after signing the ICF and prior to dosing on Day 1 will be considered Baseline signs/symptoms. The TEAE reporting period begins with administration of the first dose of study medication on Day 1 and continues until 3 weeks (21 days) after last dose of study drug. The follow-up AE reporting period begins 21 days after the last dose of study drug through completion of the Follow-up Period (Week 48 or premature withdrawal). All Baseline signs/symptoms, TEAEs and AEs during the Follow-up Period must be recorded in the source documents and on the subject's eCRF. All AEs and SAEs that occur from the signing of informed consent through Week 48 will be recorded.

If the Investigator observes an SAE after study completion that he/she believes was possibly caused by the study medication, the Investigator will report this SAE using the procedures described in Section 9.5.7.1.5.

Detailed information regarding all SAEs must also be recorded on the Serious Adverse Event Reporting Form. Whenever possible, the Investigator should group together into a single term the signs and symptoms that constitute a single diagnosis. For example, cough, rhinitis and sneezing might be grouped together as "upper respiratory infection" if the Investigator is confident of the diagnosis.

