#### Study Design:

This is a randomized, double-blind, placebo-controlled, repeat-dose, multicenter study. Subjects will be screened for the study within 4 weeks prior to the Baseline (Day 1) Visit. Approximately 25 subjects who meet the study eligibility criteria will be randomized on Day 1 in a 3:2 ratio to receive 8 infusions of TEPEZZA (10 mg/kg for the first infusion and 20 mg/kg for the remaining 7 infusions) or placebo q3W. During the 24-week double-blind Treatment Period, study drug will be infused on Day 1 (Baseline) and Weeks 3, 6, 9, 12, 15, 18 and 21 with a comprehensive visit at Week 24 (end of treatment). All study drug dosing will be performed at the clinic or infusion center under the supervision of clinic staff or nurses. At any scheduled infusion, the infusion rate may be reduced or the dose may be interrupted or held based on tolerability (see Section 9.4.6.3.2 for details). On each dosing day, scheduled assessments (except for adverse event [AE] and concomitant medication use monitoring, which will be monitored throughout the clinic visit) will be completed prior to study drug infusions. After each of the first 2 infusions, subjects will be contacted by phone/email the following day. Additional phone/email contacts and clinic visits may also be conducted for any subject experiencing an infusion-associated event.

[figure not shown]
At the end of the Treatment Period (Week 24), subjects will enter a 24-week Follow-up Period, during which study drug will not be administered and a clinic visit will be scheduled for Weeks 28, 36 and 48. A phone call or email at Weeks 32 and 42 will occur to inquire how the subject is doing and women of childbearing potential will be asked if they have missed a menstrual cycle and will have a serum pregnancy test, if required.

Subjects who prematurely discontinue prior to completing the Treatment Period will return to the clinic and undergo the scheduled Week 24 assessments; such subjects will also be encouraged to continue in the 24-week Follow-up Period. An overview of the study design is presented in the schematic below and details of study activities are provided in Section 2.1, Schedule of Assessments.

Horizon Therapeutics U.S.A., Inc. TEPEZZA (teprotumumab-trbw; HZN-001)

Date: 02 February 2022

Protocol: HZNP-TEP-001 IND 147532 Version 5.0, Amendment 4

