- 14. Serum pregnancy test at Screening and Week 48 (or as needed). Urine pregnancy tests prior to dosing at all other visits, as applicable. Perform for female subjects of childbearing potential (including those with an onset of menopause <2 years prior to Screening, non-therapy-induced amenorrhea for <12 months prior to Screening or not surgically sterile [absence of ovaries and/or uterus]).
- 15. Vital signs (blood pressure, heart rate, respiratory rate, temperature) will be measured at all clinic visits. Vital signs will be measured pre- and post-infusion on Day 1 and Week 3 and pre-infusion on all other dosing days. Additional vital signs will be monitored if infusion-associated AEs occur (see Section 9.5.7.4 for details).
- 16. Additional ECGs will be assessed, as needed.
- 17. **CCI**
- 18. HbA1c must be ≤8.0% for randomization. If the HbA1c is elevated and considered clinically significant at any time point after Screening, it will be repeated approximately every 90 days until it returns to normal or Baseline value.
- 19. Blood samples for immunogenicity testing will be collected pre-infusion on Day 1 and Weeks 3, 12 and 18; a single sample will be collected at Weeks 24, 36 and 48. If a sample is ADA positive after confirmatory and reactive titer testing, the sample will then be tested for NAb.
- 20. AEs that occur after signing the informed consent form and prior to dosing on Day 1 will be considered Baseline signs/symptoms. AEs occurring or worsening after initiation of the infusion on Day 1 through 3 weeks (21 days) after last dose of study drug will be considered treatment-emergent AEs. AEs occurring after 3 weeks (21 days) after last dose of study drug through Week 48 will be considered follow-up AEs. All AEs and SAEs that occur from the signing of informed consent through Week 48 will be recorded.
- 21. CCI
- 22. PK samples will be collected pre- and post-infusion on Day 1 and Weeks 3, 12 and 18; a single sample will be collected at Weeks 24 and 36.
- 23. **CC**

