Increase in blood glucose is a known AE observed in previous clinical trials with TEPEZZA and other IGF-1R antagonists and is known to respond to treatment. Fasting glucose levels (after at least an 8-hour fast) should be tested at Baseline. Hyperglycemia should be promptly investigated and managed. Subjects with recurrent hyperglycemia, defined as a fasting glucose level of ≥126 mg/dL (7.0 mmol/L) or higher, will require evaluation for diabetes mellitus (e.g., fasting glucose, glucose tolerance and HbA1c tests) and appropriate medical management at the discretion of the Investigator [American Diabetes Association, 2019b].

Since a referral for treatment of hyperglycemia may take some time, if the Investigator considers it appropriate to continue the subject in the study, the next scheduled infusion visit may be skipped to allow modified anti-diabetic treatment to show its activity and hyperglycemia to return to mild/moderate level before dosing. The subject would then be dosed at the next scheduled visit (i.e., 6 weeks after the previous infusion). Fasting blood glucose levels must return to mild/moderate severity before the next scheduled infusion. The above process of withholding a scheduled infusion will be permitted only twice during the study.

Any changes to the scheduled dosing interval (q3W) or adjustments in the infusion rate should be reported to the Sponsor/CRO.

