### **9.5.9.2.9** Week **24** (End of Treatment)

Week 24 is the final visit of the Treatment Period. Study drug is not administered.

- Perform physical examination, including measuring of weight.
- Query subjects regarding AEs and concomitant medications.
- Collect blood samples for hematology and chemistry (including glucose, CCl and HbA1c) analysis.
- Collect blood samples for ADA/NAb immunogenicity testing.
- CCI
- Collect blood samples for PK analyses.
- CCI
- Collect urine sample for urinalysis and also for pregnancy testing for females of childbearing potential.
- Measure vital signs.
- CCI
- Enter visit data in the EDC system.

Subjects will be discharged from the study center after all of the Week 24 procedures have been completed and will enter the Follow-up Period. Subjects will be instructed to return for a clinic visit at Week 28.

If a subject prematurely discontinues from the study during the Treatment Period, he/she will be instructed to return for a clinic visit and undergo the Week 24 assessments.

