## 9.6 Statistical Methods and Determination of Sample Size

### 9.6.1 Endpoints

# 9.6.1.1 Primary Endpoint

The proportion of subjects who experience a TEAE (as defined by National Cancer Institute Common Terminology Criteria for Adverse Events [NCI-CTCAE]) through Week 24 in subjects with dcSSc.

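### Do the protocol's adverse event periods and its rule on withheld infusions leave the end of the treatment-emergent period undecided?

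*Protocol*

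**What the plan says.** The end of the TEAE period is given twice in the protocol, each time relative to the last dose.

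- Section 9.5.7.1.2: the TEAE period "continues until 3 weeks (21 days) after last dose of study drug". The next sentence reads "The follow-up AE reporting period begins 21 days after the last dose of study drug".
- Section 2.1, footnote 20: events "through 3 weeks (21 days) after last dose of study drug will be considered treatment-emergent AEs", and "AEs occurring after 3 weeks (21 days) after last dose of study drug through Week 48 will be considered follow-up AEs".

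The primary endpoint (section 9.6.1.1) is the proportion of subjects with a TEAE "through Week 24 in subjects with dcSSc".

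Three places bear on when the last dose can fall.

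- Synopsis, Study Design: "study drug will be infused on Day 1 (Baseline) and Weeks 3, 6, 9, 12, 15, 18 and 21". Section 9.1 and the Schedule of Assessments agree.
- Section 9.4.6.3.2 allows an infusion visit to be skipped for hyperglycemia, at most twice: "The subject would then be dosed at the next scheduled visit (i.e., 6 weeks after the previous infusion").
- Section 9.5.9.2.9: "Week 24 is the final visit of the Treatment Period. Study drug is not administered".

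Section 9.5.7.1.2 also has every adverse event from consent through Week 48 recorded, and section 9.4.10 has infusion start and stop times entered in the eCRF. SAP sections 3, 6 and 7 say that 3 subjects had enrolled when the trial was stopped, that no statistical analysis will be done, and that by-subject listings will show the data as reported.

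**The concern.** The primary endpoint counts TEAEs, so the period that makes an event treatment-emergent should have one end date per subject. Two things appear to prevent this.

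First, the two definitions treat day 21 after the last dose differently. On nominal dates that day is the Week 24 visit, when subjects are asked about adverse events, examined, and have chemistry and HbA1c drawn. An event first noted then would be treatment-emergent under one text and possibly not under the other.

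Second, suppose the Week 21 infusion is withheld. The skip rule, taken word for word, leads to an infusion at Week 24, while the visit description and the infusion schedule have none there. The last dose would be Week 18 or Week 24 depending on the passage a site followed, and the TEAE period would end on different dates. Events between those dates could enter or leave the counts of TEAEs by preferred term, grade, seriousness and relatedness planned in section 9.6.3.4.

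A smaller gap adds to this: section 9.6.1.1 does not say whether Week 24 means a fixed study day or the date of the visit.

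**Working it through.** **Numbering.** The first infusion is on Day 1, so the Week w visit falls nominally on study day 7w + 1.

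**Planned course.** Last dose at Week 21: 7 × 21 + 1 = 148. End of TEAE period: 148 + 21 = 169. Week 24: 7 × 24 + 1 = 169. The 21-day rule therefore closes the period exactly at the end-of-treatment visit, as the design intends.

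**Which skipped infusions cause trouble.** If the infusion at Week s is skipped, the previous one was at Week s − 3, and six weeks after that is Week s + 3.

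| Skipped | Six weeks after previous infusion | Planned infusion visit? |
|---|---|---|
| Week 3 | Week 6 | yes |
| Week 6 | Week 9 | yes |
| Week 9 | Week 12 | yes |
| Week 12 | Week 15 | yes |
| Week 15 | Week 18 | yes |
| Week 18 | Week 21 | yes |
| Week 21 | Week 24 | no |

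Only the last of the seven conflicts with the schedule.

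**Size of that conflict.**

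- No infusion at Week 24: last dose at Week 18, day 7 × 18 + 1 = 127; period ends on day 127 + 21 = 148 (Week 21).
- Infusion at Week 24: last dose on day 169; period ends on day 169 + 21 = 190 (Week 27).
- Difference: 190 − 148 = 42 days. Of these, 169 − 148 = 21 days lie before Week 24, and 21 / 168 = 12.5% of the 24-week window. The other 21 days lie after Week 24 and cannot enter the primary endpoint.

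Neither section 9.4.6.3.2 nor section 9.5.9.2.9 names Week 18 or Week 24 as a last dose; both dates are inferred from the wording.

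**Day 21 after the last dose.**

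| Text | TEAE on day 21? | Follow-up on day 21? |
|---|---|---|
| Footnote 20 | yes | no |
| Section 9.5.7.1.2, end point inclusive | yes | yes |
| Section 9.5.7.1.2, end point exclusive | no | yes |

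The two texts differ on this day under either reading of section 9.5.7.1.2. They agree on every other day.

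**Meaning of Week 24 for a completer.** Let the Week 21 dose fall on day 148 + u, with u from −3 to 3, and the Week 24 visit on day 169 + v, with v from −7 to 7. The TEAE period ends on day 169 + u. It can outlast a fixed Day 169 by at most 3 days, and the visit date by at most 3 − (−7) = 10 days.

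**Effect on the primary yes/no.** A subject reaches the withheld-Week-21 case because of hyperglycemia during treatment, which would normally already be a TEAE. That subject counts under either end date. The day-21 wording matters only for a subject whose first TEAE begins on exactly that day. The Week 24 gap matters only for a completer whose first TEAE falls in those few days.

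**The case for a change.** The best case for editing the text is that both conflicts are real on the page and cheap to remove. The day-21 mismatch survives either reading of section 9.5.7.1.2, falls nominally on the primary analysis time point, and is not settled by the SAP, which repeats the endpoint without defining a TEAE. On withheld infusions, section 9.4.6.3.2 makes no exception for Week 21, and its six-week interval points to Week 24. If its wording is read instead as the next infusion visit, the section gives no instruction for this case. The counts in section 9.6.3.4 could differ even where the primary yes/no does not.

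The textual observations stand. The claim that the protocol contradicts itself on the TEAE period does not. Both definitions use 21 days after the last dose, and that date is meant to move with exposure. Under one passage the subject receives a further infusion and under the other does not, so the periods differ because treatment differs. Once infusion dates are recorded, the end date is fixed whichever passage the site followed. The inconsistency lies in the dosing text, not in the endpoint definition.

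On day 21, an analyst needs a non-overlapping rule and footnote 20 supplies one. No event is lost under either text, because collection runs to Week 48. The counts that might have shifted will not be produced under the SAP.

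**Conclusion.** No change to the analysis plan is warranted. The day-21 point is a one-day wording slip with a clean rule already in footnote 20. The open meaning of Week 24 is worth at most 3 days against a fixed day, or 10 against the visit date, and only for late events in completers.

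The withheld-infusion point is a literal inconsistency between section 9.4.6.3.2 and section 9.5.9.2.9 with the infusion schedule. It is confined to one of seven possible skips and carries through to a 42-day difference in the end of the TEAE period, 21 days of it inside the primary window. Those passages must be reconciled if they are to guide dosing again; no view is taken on which should prevail.

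The conclusion rests on four things: the 21-day rule is common to both definitions; infusion times and all adverse events through Week 48 are recorded; the hyperglycemia behind a withheld infusion is normally itself a TEAE; and the SAP limits reporting to listings for 3 subjects. It also assumes that those listings let a reader set event onset against dosing dates, which the SAP does not spell out. The documents give no rate for withheld Week 21 infusions, so their frequency cannot be estimated. No direction of bias follows, and no planned result changes.

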#### 9.5.7.1.3 Intensity of Adverse Events

All clinical AEs encountered during the study will be reported on the AE form of the eCRF. Intensity of AEs will be graded on a 5-point scale (mild, moderate, severe, life-threatening, death) and reported in detail on the eCRF.

Date: 02 February 2022

IND 147532

TEPEZZA (HZN-001) Protocol: HZNP-TEP-001 Version 5.0, Amendment 4

Intensity	Definition	Corresponding NCI-CTCAE Grade		
Mild	discomfort noticed but no disruption of normal daily activity	1		
Moderate	discomfort sufficient to reduce or affect daily activity	2		
Severe	inability to work or perform normal daily activity	3		
Life-threatening	represents an immediate threat to life	4		
Fatal	results in death	5		

NCI-CTCAE=National Cancer Institute Common Terminology Criteria for Adverse Events

# 9.5.7.1.4 Relationship to Study Drug

The relationship of the study drug to each AE will be determined by the Investigator and the Sponsor based on the following definitions:

- No reasonable causal relationship (not related): There is no plausible temporal relationship or there is another explanation that unequivocally provides a more plausible explanation for the event.
- Yes, reasonable causal relationship (possibly related): There is evidence in favor of a causal relationship (i.e., there is a plausible time course) and at least one of the following criteria apply:
  - There is a reasonable pharmacological relationship (or known class effect).
  - There is no other more plausible explanation.
  - There is a positive de-challenge (without active treatment of the event).
  - There is a positive re-challenge.
  - There is a distinguishable dose effect.

Within the reporting requirement under 21 CFR 312.32I(1)(i), the FDA provides the following examples of types of evidence that would suggest a causal relationship between the drug and the AE.

- A single occurrence of an event that is uncommon and known to be strongly associated with drug exposure (e.g., angioedema, hepatic injury, Stevens-Johnson Syndrome).
- One or more occurrences of an event that is not commonly associated with drug exposure, but is otherwise uncommon in the population exposed to the drug (e.g., tendon rupture).

Date: 02 February 2022

IND 147532

TEPEZZA (HZN-001) Protocol: HZNP-TEP-001 Version 5.0, Amendment 4

 An aggregate analysis of specific events observed in a clinical trial (such as known consequences of the underlying disease or condition under investigation or other events that commonly occur in the study population independent of drug therapy) that indicates those events occur more frequently in the drug treatment group than in a concurrent or historical control group.

## 9.5.7.1.5 Reporting and Documenting Serious Adverse Events

All SAEs beginning with the time of signing of the ICF and continuing through Week 48 (end-of-study visit) must be reported. The following steps will be taken to report promptly and document accurately any SAE, whether or not it appears to be related to the study medication:

- Report the SAE to the Sponsor by entering the information into the eCRF within
   24 hours after becoming aware that a subject has experienced an SAE. If unable to access the eCRF, the event must be reported by submitting the completed SAE form by email to [contact], fax or telephone within
   24 hours after becoming aware that a subject has experienced an SAE (see Appendix 17.1 for contact information).
- 2. Perform appropriate diagnostic tests and therapeutic measures and submit all follow-up substantiating data, such as diagnostic test reports, hospital discharge summaries and autopsy report to the Sponsor's representative.
- 3. Respond in a timely manner to any queries from Sponsor regarding the SAE.
- 4. Conduct appropriate consultation and follow-up evaluation until the SAE is resolved, stabilized or otherwise explained by the Investigator.
- 5. Review each SAE report and evaluate the relationship of the SAE to study treatment. The Sponsor will determine whether the SAE is unexpected in nature.
- 6. The Investigator must report all AEs or SAEs that meet the criteria for Unanticipated Problems Involving Risks to Human Subjects or Others to the IRB/IEC.

## 9.5.7.1.6 Follow-up of Adverse Events

Any ongoing study drug-related AE present at the time of study termination, including a clinically significant laboratory test abnormality, will be followed until resolved or until the event stabilizes and the overall clinical outcome has been ascertained.

In the event of unexplained, treatment-emergent, clinically significant abnormal laboratory test results or clinically significant changes in laboratory test results, the tests should be repeated immediately and followed until the values have returned to within the reference range or to Baseline for that subject.

TEPEZZA (HZN-001) Protocol: HZNP-TEP-001 Version 5.0, Amendment 4

#### 9.5.7.1.7 Medication Errors

A medication error is any unintended failure in the drug treatment process, such as mistakes in the prescribing, dispensing, storing, preparation or administration of a medicine that leads to, or has the potential to lead to, harm to the patient.

All cases of medication errors, which include overdose, will be documented on the eCRF in order to capture this important safety information consistently in the database. AEs associated with a medication error, such as an overdose, or an SAE of overdose are to be reported according to the procedures outlined in Sections 9.5.7.1.2 and 9.5.7.1.5, respectively.

An overdose is defined as a known deliberate or accidental administration of investigational drug to a subject. For this study, any dose of TEPEZZA that is greater than 27 mg/kg q3W over the dose that has been assigned will be considered an overdose.

In the event of drug overdose, the subject is to be treated with symptomatic and supportive care, as required.

## 9.5.7.1.8 Review of Adverse Events and Emerging New Safety Information

The Sponsor will perform an ongoing review of all AEs and all other emerging new information relevant to the safety of the drug, including periodic review and analyses of their entire safety database.

## 9.5.7.1.9 Reporting of Investigational New Drug Safety Reports

The Sponsor will notify the US FDA and all Investigators of any new serious risks associated with the drug.

